6.1. Screening

Screening is the interval between signing the ICF and the day the subject is enrolled in the study (eg, Cycle 1 Day 1). Screening may not exceed 28 days. Informed consent must be obtained before performing any study-specific procedures that are not considered standard of care; however, procedures conducted as part of the subject's routine clinical management obtained before signing of informed consent may be used for screening or baseline purposes with approval of the medical monitor, provided that the procedure meets the Protocol-defined criteria and has been performed in the timeframe of the study. Assessments that are required to demonstrate eligibility may be performed over the course of 1 or more days during the screening process.

Results from the screening visit evaluations will be reviewed to confirm subject eligibility before enrollment. Tests with results that fail eligibility requirements may be repeated **once** during screening if the investigator believes the results to be in error. For screening assessments that are repeated, the most recent available result before enrollment will be used to determine subject eligibility. Additionally, a subject who fails screening may repeat the screening process **1 time** if the investigator believes there has been a change in eligibility status (eg, after recovery from an infection). Treatment should start as soon as possible after the date of enrollment.

6.2. Treatment

The treatment period begins on the day the subject receives the first dose of study treatment (Cycle 1 Day 1) through the point at which the investigator determines that the subject will be permanently discontinued from study treatment. Cycle 1 Day 1 must be no more than 28 days after the subject has signed the ICF and should be within 3 days of enrollment in the study. Subjects will have regularly scheduled study visits as outlined in [Table 12](#), and toxicities will be monitored continuously and will be graded using the NCI CTCAE v4.03 criteria.

6.3. End of Treatment

When the subject permanently discontinues study treatment, the EOT visit should be conducted. If the EOT visit coincides with a regular study visit, the EOT evaluations will supersede those of that scheduled visit, and the data should be entered in the EOT visit in the eCRF. The subject should be encouraged to return for the safety follow-up visits.

6.4. Safety Follow-Up

The safety follow-up period is the interval between the EOT visit and the scheduled follow-up visit, which should occur 30 days (+ 7 days) and 60 days (+ 7 days) after the last dose of study treatment. Monitoring for the occurrence of new AEs should be continued for at least 60 days after the last dose of study treatment or until the start of new anticancer therapy, whichever occurs first. Reasonable efforts should be made to have the subject return for the follow-up visits and report any AEs that may occur during this period. If a subject is scheduled to begin a new anticancer therapy before the end of the 30-day or 60-day safety follow-up period, the safety follow-up visit should be performed before new anticancer therapy is started. Once new anticancer therapy has been initiated, AEs and SAEs will no longer be collected and the subject will be considered to have completed the study.

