5.4.7. Management of Immune-Related Adverse Events

Nivolumab and ipilimumab are immune checkpoint inhibitors and are known to induce irAEs. INCAGN01949 is an immune modulator that may enhance the activity of other immunotherapies and therefore may also exacerbate any irAEs associated nivolumab and ipilimumab. Adverse events of a potential immunologic etiology or irAEs may be defined as an AE consistent with an immune phenomenon associated with drug exposure **after all other etiologies have been ruled out**. Immune-related AEs may be expected based on the nature of the study treatment, their mechanism of action, and reported experience with these and other immunotherapies. Special attention should be paid to AEs that may be suggestive of potential irAEs. An irAE can occur shortly after the first dose or several months after the last dose of treatment. Suspected irAEs should be discussed with the medical monitor when possible.

Subjects should receive appropriate supportive care measures as deemed necessary by the treating investigator. Suggested supportive care measures for the management of drug-related AEs with potential immunologic etiology are outlined in [Table 10](#). Detailed supportive care guidelines for specific irAEs can be found in [Appendix B](#). Nivolumab and ipilimumab are approved therapies and have specific irAE management guidelines within their package insert; the treating investigator may use labeled guidance or institutional guidelines for the management of irAEs if preferred. For each AE, attempts should be made to rule out other causes, including but not limited to metastatic disease or bacterial or viral infection, which might require specific supportive care.

Table 10: Supportive Care Guidelines for Immune-Related Adverse Events

CTCAE Grade/Severity	Supportive Care ^a
1 (Mild)	
Monitor symptoms and provide symptomatic treatment.
2 (Moderate)	
Monitor symptoms and provide symptomatic treatment.Consider consultation with specialists as necessary.Consider systemic corticosteroids per institutional standard of care.

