5.5.2. Withdrawal Procedures

In the event that the decision is made to permanently discontinue the study treatment, the subject will be withdrawn, and the EOT visit should be conducted. Reasonable efforts should be made to have the subject return for all follow-up visits (see Section 6.4). The last date of the last dose of study treatment and the reason for subject withdrawal will be recorded in the eCRF.

If a subject is withdrawn from the study treatment:

- The study monitor or sponsor must be notified.
- The reason(s) for withdrawal from treatment must be documented in the subject's medical record and in the eCRF.
Note: The reason for withdrawal from treatment may be different than the reason for withdrawal from study. For example, subjects can discontinue treatment for disease progression or toxicity but remain in the study for safety follow-up.
- The EOT visit should be performed.
- The date of the EOT visit should be recorded in the eCRF and IRT.
- Subjects must be followed for safety until the time of the follow-up visit, or until study treatment-related toxicities resolve, return to baseline, or are deemed irreversible, or until the subject begins new anticancer therapy, whichever is longest.

If the subject discontinues study treatment and actively withdraws consent for collection of safety follow-up data, then no additional data collection should occur; however, **subjects will have the option of withdrawing consent for study treatment but continuing in the follow-up period of the study for safety assessments.**

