8.3.2. Reporting

Every SAE, regardless of suspected causality (eg, relationship to study drug(s) or study procedure or disease progression), occurring after the subject has signed the ICF through the last study visit (or 60 days after the last dose of study treatment, or until the subject receives a new anticancer therapy whichever occurs earlier) must be reported to the sponsor (or designee) within **24 hours** of learning of its occurrence, unless otherwise specified by the Protocol. Any SAEs occurring more than 60 days after the last dose of study treatment should be reported to the sponsor or its designee only if the investigator suspects a causal relationship to the study drug.

Information about all SAEs is collected and recorded on the Adverse Event form of the eCRF. The investigator must assess and record the causal relationship of each SAE to each specific study treatment. The investigator must also complete the Incyte Serious Adverse Event Report Form, in English, and send the completed and signed form to the sponsor or designee within 24 hours of becoming aware of the SAE. The investigator must provide a causality assessment, that is, assess whether there is at least a reasonable possibility that the SAE is related to the specific study treatment: suspected (yes) or not suspected (no). Refer to the Incyte Reference Guide for Completing the Serious Adverse Event Report Form.

The contact information of the sponsor's study-specific representatives is listed in the investigator manual provided to each site. The original copy of the SAE Report Form and the confirmation sheet must be kept at the study site.

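### Protocol 6.4 ends all AE and SAE collection at new anticancer therapy, against the protocol's own rules for unresolved related toxicity and late related SAEs

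*Protocol*

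**What the plan says.** Protocol 6.4 has monitoring for new AEs run for "at least 60 days after the last dose of study treatment or until the start of new anticancer therapy, whichever occurs first". It asks that the safety visit be held before any new anticancer therapy begins. After that therapy begins, "AEs and SAEs will no longer be collected and the subject will be considered to have completed the study". It makes no exception for events that are unresolved, related or serious.

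Other sections set different limits:

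- **5.5.2:** "Subjects must be followed for safety until the time of the follow-up visit, or until study treatment-related toxicities resolve, return to baseline", or are judged irreversible, "or until the subject begins new anticancer therapy, whichever is longest".
- **8.1.2:** an AE, once detected, is followed to resolution or permanence, with severity, causality, treatment and outcome reassessed. New therapy is not a limit.
- **5.4.4:** a DLT is followed to baseline or until stable for at least 4 weeks. New therapy is not a limit.
- **8.3.2:** the routine SAE window runs to the last visit, or 60 days after last dose, "or until the subject receives a new anticancer therapy whichever occurs earlier". SAEs later than 60 days "should be reported to the sponsor or its designee only if the investigator suspects a causal relationship to the study drug". New therapy is not mentioned there. Recurrence or progression of a reported SAE is reportable without time limit.

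SAP 8.2.1 starts the treatment-emergent period at first dose and gives it no end. AEs count as treatment-emergent unless they clearly are not.

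**The concern.** Frequency, duration and severity of AEs form the primary safety endpoint (Protocol 2.2.1). With Phase 2 cancelled, only the Phase 1 analyses of the 52 enrolled subjects remain (Section 9). Section 5.4.7 warns that "An irAE can occur shortly after the first dose or several months after the last dose of treatment", and 5.4.2 allows toxicity seen after the DLT period to lower the MTD.

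A site that follows 6.4 closes the record at new therapy. A site that follows 5.5.2, 8.1.2 or the late-SAE sentence of 8.3.2 keeps reporting. The same clinical course can then produce different data. Section 4.5 does not help: for subjects still on study after an early database lock it sends investigators to both Section 8 and 6.4. The SAP does not settle the matter either, because its treatment-emergent period has no end.

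**Working it through.** The plan states no figure on this point, so the check sets the sections against four cases. Days count from last dose and are chosen for illustration.

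| Case | 6.4 | Other sections | Result |
|---|---|---|---|
| 1. Related Grade 3 AE unresolved when new therapy starts on day 20 | Not collected | 5.5.2 and 8.1.2: follow on (5.4.4 too if a DLT) | Conflict |
| 2. New therapy day 30, suspected related SAE day 75 | Not collected | 8.3.2: reportable | Conflict |
| 3. New therapy day 30, suspected related SAE day 45 | Not collected | 8.3.2: routine window closed on day 30; late sentence starts after day 60 | Gap |
| 4. New therapy day 30, new non-serious AE day 45 | Not collected | 8.1.2: monitoring for new AEs has ended | Agreement |

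Case 1 turns on 5.5.2 taking the longest of its limits, so new therapy alone cannot end follow-up while related toxicity is open.

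Case 2 matters for analysis because 8.3.2 puts every SAE on the AE form of the eCRF.

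Case 3 lasts 60 − d days when new therapy starts on day d: 60 − 30 = 30 days here, and 40 days for d = 20. A suspected related SAE in that interval falls under neither sentence of 8.3.2, yet becomes reportable if it occurs after day 60.

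Case 4 is not reopened by the follow-up-visit limit in 5.5.2, since 6.4 and 7.5 place that visit before new therapy.

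**Size.** The documents give neither the share of subjects starting new therapy (s) nor the share of those with case 1, 2 or 3 data outstanding (r). With N = 52, the expected number affected is 52 × s × r. On assumed ranges of s from 20% to 60% and r from 2% to 10%:

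- Low end: 52 × 0.20 × 0.02 = 0.2 subjects; chance of at least one = 1 − 0.98^10 = 0.18.
- High end: 52 × 0.60 × 0.10 = 3.1 subjects; chance of at least one = 1 − 0.90^31 = 0.96.

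These ranges have no basis in the documents. They show only that the size is undetermined. Using 52 also overstates the reach of a wording change now, because it can help only subjects still being followed, and their number is not given.

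**The case against.** Much of the protocol is consistent here. The new-AE window in 8.1.2 and the routine SAE window in 8.3.2 stop at new therapy just as 6.4 does. The Amendment 2 summary presents the new-AE stop as a deliberate clarification. There is a sound reason for it: after a new agent starts, attribution of new events is confounded. The visit held before new therapy records AE status before the record closes. Section 7.6.1 also refers readers to Section 8 for reporting rules, which include the late-SAE sentence. All of this stands, and it supports keeping a cutoff for new AEs. It does not cover toxicity whose onset precedes the new therapy, or SAEs the investigator still suspects are related.

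The effect on the planned tables is also limited. SAP 8.2.4 and its Appendix A count subjects by term and maximum severity, and no table of AE duration is listed. In case 1 the event is already counted at Grade 3. Stopping follow-up changes no count unless the event worsens or becomes fatal; otherwise the loss shows only in listings.

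It could be said that following a subject is clinical care rather than data collection. That reading is hard to hold against 8.1.2, which asks for outcome and changes in severity to be assessed, or against 6.4, which treats the subject as having completed the study.

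**Conclusion.** The contradiction is real and should be removed. Section 6.4 forbids collecting two kinds of data that other sections require: the duration and outcome of related toxicity already detected when new therapy starts, and suspected related SAEs after day 60. The day-60 gap within 8.3.2 is a further defect. The direction is under-recording at sites that follow 6.4. The size cannot be fixed from the documents. The 28-day DLT window is largely unaffected.

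Two stronger readings are tempting. A reader might infer that this conflict makes the primary endpoint lose delayed immune-related events in general. It does not: no section requires new non-serious events after the window, so that loss comes from the common cutoff.

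A reader might also multiply 52 by an assumed 30% to 60% of early starters, giving 16 to 31 subjects (15.6 and 31.2), and call these affected. That counts subjects whose routine window closes early under every section. Only those among them with outstanding related toxicity or a later suspected related SAE are in dispute.

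**What to change.** In Protocol 6.4, limit the effect of new anticancer therapy to ending collection of new AEs. State that ongoing related AEs are still followed as in 5.5.2 and 8.1.2, that DLTs are followed as in 5.4.4, and that suspected related SAEs remain reportable whenever they occur. Say explicitly that worsening of an ongoing related AE is follow-up, since 8.1.2 records each change in severity as a separate AE.

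Amend 8.3.2 so that suspected related SAEs between new therapy and day 60 are covered. Align 8.1.2, which is not restricted to related events, by stating whether unrelated ongoing AEs close at new therapy.

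In SAP 8.2.1, end the treatment-emergent window at the earlier of 60 days after last dose and new anticancer therapy, and list later related events separately. The summary tables are then comparable across sites, and the late events stay visible without mixing in events that may belong to the new agent.

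The cost is wording in both documents and minor extra site reporting. No visits are added.

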6.5. End of Study

The end of the study will occur when all subjects have completed the last study follow-up visit or have discontinued study treatment and have completed applicable follow-up assessments.

Additionally, subjects will be considered as having completed the study if they meet any of the following criteria:

- Subject dies and a date of death is available.
- Subject is known to have died; however, the date of death cannot be obtained.
(NOTE: Every effort must be made to obtain the date of death.)
- Consent is withdrawn for any further contact related to this study.
 - Every reasonable effort should be made to determine the reason a subject withdraws prematurely, and this information should be recorded in the eCRF.
- The study is terminated by the sponsor.
- The study is terminated by the local health authority or IRB or IEC.

6.6. Unscheduled Visits

Unscheduled study visits may occur at any time if medically warranted. Any assessments performed at those visits should be recorded in the eCRF.

7. CONDUCT OF STUDY ASSESSMENTS AND PROCEDURES

Individual study procedures are described in detail below. It may be necessary to perform these procedures at unscheduled timepoints if deemed clinically necessary by the investigator. Furthermore, additional evaluations/testing may be deemed necessary for reasons related to subject safety. In some cases, such evaluation/testing may be potentially sensitive in nature (eg, HIV, HCV), and thus local regulations may require that additional informed consent be obtained from the subject. In these cases, such evaluations/testing will be performed in accordance with those regulations. Subjects of childbearing potential must agree to take appropriate measures to avoid pregnancy in order to participate in the study ([Appendix A](#)).

7.1. Administration of Informed Consent Form

Valid informed consent must be obtained from the study subject before conducting any study-specific procedures using an ICF approved by the local IRB/IEC that contains all elements required by ICH E6 and describes the nature, scope, and possible consequences of the study in a form understandable to the study subject. Local and institutional guidelines for ICF content and administration must be followed; the original signed ICF must be retained by the investigator, and a copy of the signed ICF must be provided to the study subject. The informed consent process for each subject must be documented in writing within the subject source documentation.

7.2. Interactive Response Technology System Procedure

The site will contact the IRT to obtain a subject identification number when a subject enters the prescreening phase. Upon determining that the subject is eligible for study entry, the IRT will be contacted to obtain the subject number and treatment group assignment. Additionally, the IRT will be contacted to update the subject's disposition and disease response and for study drug resupply. Refer to the IRT manual for detailed instructions.

7.3. Demography and Medical History

7.3.1. Demographics and General Medical History

Demographic data and a complete medical and medication history will be collected at screening by the investigator or qualified designee and will include date of birth, race, ethnicity, medical and surgical history, and current illnesses. Medical history will include relevant medical or surgical treatment **within the last 10 years that are considered to be clinically significant** by the investigator.

7.3.2. Disease Characteristics and Treatment History

A disease-targeted medical and medication history will be collected at screening. Details regarding the subject's malignancy under study including date of diagnosis, initial and current cancer stage, tumor histology, relevant disease characteristics, and prior treatments including systemic, radiation, and surgical procedures will be recorded.

7.4. Prior and Concomitant Medications and Procedures

Prior and concomitant medications and procedures will be reviewed to determine subject eligibility. Any medication received or procedure performed within 28 days before the first dose of study treatment, up to the end of the safety follow-up phase, or until the subject starts a new anticancer therapy, whichever occurs first, will be recorded in the eCRF. The medication record will be maintained after signing the ICF to document concomitant medications, including any changes to the dose or regimen. Concomitant medications include any prescription, over-the-counter, or natural/herbal preparations taken or administered during the study period. Concomitant treatments and/or procedures that are required to manage a subject's medical condition during the study will also be recorded in the eCRF. See Section [5.6](#) for details regarding restricted and prohibited medications.

7.5. Poststudy Anticancer Therapy Status

The investigator or qualified designee will review all new anticancer therapy initiated after the last dose of study treatment. If a subject initiates a new anticancer therapy within 30 to 60 days after the last dose of study treatment, the 30-day or 60-day safety follow-up visit should occur before the first dose of the new anticancer therapy.

7.6. Safety Assessments

7.6.1. Adverse Events

Adverse events will be monitored from the time the subject signs the ICF. Subjects will be instructed to report all AEs during the study and will be assessed for the occurrence of AEs throughout the study. In order to avoid bias in eliciting AEs, subjects will be asked general, nonleading questions such as "How are you feeling?" All AEs (serious and nonserious) must be recorded on the source documents and eCRFs regardless of the assumption of a causal relationship with the study drug. The definition, reporting, and recording requirements for AEs are described in Section [8](#).

7.6.2. Physical Examinations

Physical examinations must be performed by a medically qualified individual such as a licensed physician, physician's assistant, or an advanced registered nurse practitioner, as local law permits. Clinically notable abnormalities that are considered clinically significant in the judgement of the investigator are to be reported as AEs.

7.6.2.1. Comprehensive Physical Examination

The comprehensive physical examination will include assessment(s) of the following organ or body systems: skin; head, eyes, ears, nose, and throat; thyroid; lungs; cardiovascular system; abdomen (liver, spleen); extremities; and lymph nodes, as well as a brief neurological examination. The screening physical examination should also include a measurement of height.

7.6.2.2. Targeted Physical Examination

The targeted physical examination will be a symptom-directed evaluation conducted by the investigator or a medically qualified designee. The targeted physical examination will include assessment(s) of the body systems or organs, as indicated by subject symptoms, AEs, or other findings.

7.6.3. Vital Signs

Vital sign measurements include blood pressure, pulse, respiratory rate, and body temperature. Blood pressure and pulse will be taken with the subject in the recumbent, semirecumbent, or sitting position after 5 minutes of rest. Weight will also be assessed at each study visit. Clinically notable abnormalities that are considered clinically significant in the judgment of the investigator are to be reported as AEs.

